## **7.10 Neonates discharged home from the participating unit**

Data collection will cease and an End of Study Form will be completed at the time of death, discharge home, 38 weeks CGA or at Study Day 28 if this is later (for those neonates recruited after 34 weeks CGA). For those occasional neonates who are discharged home before Study

Day 28 a telephone call follow up by the local research team will be made to determine if there were any serious adverse events at Study Day 28. Prior consent will be sought to contact the parents / GP/ Health Visitor for this information

### **7.11 Cranial ultrasound scans**

Each centre must have the capability to conduct cranial USS at any time, 24 hours a day. Cranial USS required are as follows:

- a) Within 6 hours prior to randomisation
- b) Thereafter, a minimum of weekly USS (+/-3 days) should be performed until study day 28 or prior to discharge if earlier
- c) For neonates who remain in hospital longer than 28 days, any scan performed should be recorded in the weekly assessment form and a final USS should be done prior to discharge.

The data to be collected from the USS reports and recorded in the bleeding assessment tool / weekly assessment forms (to be filled in as per the guidance of the bleeding assessment record guidance notes) are as follows:

- Evidence of intracranial haemorrhage and its extent
- Ventricular Size
- Parenchymal injury and grade.

### **7.12 Two year neuro-developmental follow-up.**

[figure not shown]
Neuro-developmental follow-up will be undertaken by validated Thames Regional Perinatal Outcome Group/ Standard Electronic Neonatal Database/ National Neonatal Audit Programme (TRPG/SEND/NNAP) 2- year corrected age outcome form and will be administered at 2 years of corrected gestational age. The results of the WHO functional disability criteria and any disability will be classified into 3 groups: mild, moderate and severe. A record of all deaths within 2 years after randomisation will be kept.

In order to obtain the 2 year follow-up data, permission will be sought to contact parents at around 2 years CGA when obtaining informed consent for the trial.

Approximately 7 – 10 days before the baby reaches 2 years corrected age a 2 year follow up questionnaire will be posted out by the site research team to the parents/guardians with a self-addressed envelope for completion. The questionnaire is the (PARCA-R) standardised assessment with additional questions adapted from the TRPG survey to obtain information regarding gross and fine motor skills. Permission to contact is outlined in the Informed Consent Form (V3.0). Further contact will be made by the Two year follow up co-ordinator if required, by telephone, email, or text if the questionnaire is not returned. A telephone interview will be offered at this time, or a weblink sent by text or email to complete the questionnaire online if preferred. The process is outlined in Fig 3

Where primary outcome and 2 year follow-up data cannot be obtained by direct contact with parents or clinicians, it may be possible to extract pseudo-anonymised information from the national neonatal database. The research team at the recruiting centre will be able to access this data.

**Fig 3 Pathway for Sending out 2 Year Follow-up Questionnaire**

### Definition for Corrected Gestational Age (CGA)

Corrected Gestational Age is defined as the age of the child from the expected date of delivery when the child is born preterm. This can be calculated as chronological age - the number of weeks the baby was born preterm.

For example, for a baby born at 28 weeks gestation who has celebrated his 2nd birthday today this would mean

24 months - [(40 weeks - 28 weeks) x 1 month/ 4 weeks] months which equates to a corrected gestational age of 21 months.

NB: In this protocol, the term "Corrected Gestational Age" is used, but its' definition is considered synonymous with the term "Post-Menstrual Age" (PMA)

### **7.13 Other assessments**

Overall figures for numbers of admissions to participating units during the active period of the study will be collected. It is expected that these data will be available from locally maintained databases on the unit. A trial screening log will be maintained for all neonates with platelet counts  $<100 \times 10^9/L$  and gestational age  $<34$  weeks at birth, to record data to include GA, post-natal age, birth weight, gender and main diagnosis.

Data will be recorded on all-cause mortality, causes of death as recorded on the death certificate, length of hospital stay, and occurrence of medical conditions such as sepsis and NEC (this is because these conditions may develop between multiple episodes of thrombocytopenia). NEC  $\geq$  Stage 2 will be defined as per Bell's criteria (Appendix B). Sepsis will be defined as culture positive sepsis or culture negative sepsis where antibiotics are given for a minimum of 5 complete days.

### **7.14 Assigning a grade (none, minor, moderate, major and severe) of bleeding using Bleeding Assessment Tool for Analysis**

The grade of bleed will be assigned centrally by means of a computer algorithm at the time of data entry. The database's bleeding algorithm will be validated by using data from pre-piloted bleeding assessment tools.

### **7.15 Withdrawal of consent**

Parents or guardians are free to withdraw their baby from the trial at any stage, and for any reason, and without having to provide any reason for their decision. Only data collected up to the time of withdrawal will be included in the analysis. An end of study form will be completed.

### **7.16 Early stopping of trial treatment allocation**

If the parents, guardians or clinicians responsible for clinical care wish to discontinue trial treatment allocation, study personnel should explain to the parents the value of complete trial data collection, and request that they allow collection of trial follow-up data (up to end of study period and 2 year developmental assessment) to continue. In this case, the neonate will not be withdrawn from the trial, but be discontinued from the randomised treatment. The early stopping of trial treatment allocation form must be completed to record this.

### **7.17 Blood results and transfusion data**

Platelet transfusion data and platelet count should be collected on a daily basis up to study day 28 (and then weekly using the weekly assessment form after Study day 14) using a transfusion data form for each patient. This will require close scrutiny of the patient's current prescription chart and liaison with the hospital blood bank. The number of red cell transfusions received from randomisation to study day 28 will also be recorded.

### **7.18 Demographic data**

Demographic data will be gathered on a screening log on all neonates with platelets  $<100 \times 10^9/L$  who are cared for in selected participating units. These data will include age, gender, GA, post-natal age and main diagnoses. They will contain no identifying information (initials/date of birth) before being sent to the CTU. The local PI or designate will be responsible for co-ordinating this data collection. These data will be used to identify the proportion of eligible babies that are recruited to the trial, as well as providing valuable

information about the population of very pre-term thrombocytopenic neonates in the participating hospitals.

## 8 SAFETY REPORTING

### 8.1 Defining safety reporting

The main *anticipated* complications for safety reporting in this trial are bleeding episodes and transfusion related adverse events. In addition, data on episodes of necrotising enterocolitis and sepsis will be collected. All safety reporting will begin from the time of randomisation and continue until the neonate completes the study.

### 8.2 Major bleeding events

Major (including severe – see definitions in Section 6.4) bleeding events will not be reported as SAEs as this is the primary outcome measure for this trial. All new major bleeding events will be reported on the specific form as soon as possible and preferably within 24 hours to the CTU using a major bleed form, and without disclosing the allocation arm. Each report will be forwarded to the DMC for review as soon as it is received at the CTU. All bleeding events will continue to be monitored and recorded in all neonates on a daily basis using the bleeding assessment form. In cases of uncertainty by the local research team about the interpretation and recording of any (major) bleed on the bleeding assessment form, the local team may contact the joint CI or one of the neonatal medical experts. The medical experts and the joint CI will form an adjudication panel for any further clarifications if necessary (excluding the local PI).

The DMC will also review regular summary reports on all bleeds produced by the trial statistician. The DMC will have a clear responsibility to advise the TSC on any concerns about these data (see section 11.3).

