## **6.7 Early stopping of the allocated treatment**

If in the clinical judgement of the attending neonatologist, an enrolled neonate cannot follow treatment allocation (e.g. a higher platelet transfusion threshold is clinically warranted), the case should be discussed with the joint chief investigator or one of the medical experts. Irrespective of the clinical decision, data collection should continue, aiming to complete data collection at least up to study day 28. Reasons for deviation from the randomised treatment allocation will be recorded.

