### 9.2 Outcome measures

#### 9.2.1 Primary outcome

The primary outcome measure is the proportion of patients who either die or develop a major or severe bleed up to and including study day 28.

This composite outcome was chosen because these endpoints represent significant clinical outcomes of relevance to the trial question.

Observation up to and including Study Day 28 was chosen for several reasons. First, in the PlaNet-1 study all major bleeds occurred within the 28 days following onset of thrombocytopenia. Secondly, primary outcome measures in many studies in this patient population are measured at Study Day 28.

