### **In cases where no imaging is performed within -5 / + 10 days of SD28:**

- If a baby is discharged home well and not readmitted prior to SD28, we will assume no MB had occurred by SD28.
- For babies discharged home after SD28, we will assume that no new major cranial bleed had taken place by SD28 if other Cranial Ultrasound (CUSS), CT or MRI scans performed on or between SD14 and discharge showed no new major bleeding providing that there was no documented episode of any significant clinical deterioration (e.g proven sepsis, NEC, or collapse) that required transfusion with blood products, or evidence of other new major bleeding in that period.
- In cases where no subsequent pre-discharge CUSS, CT or MRI scan was undertaken, providing that there is, prior to discharge, no documented episode of any significant clinical deterioration (e.g. proven sepsis, NEC, or collapse) that required transfusion with blood products, or evidence of other new major bleeding, then we will also assume that there was no major bleed at SD28.
- All other cases are to be dealt with on a case by case basis
- Review of evidence in the first case by [name], Joint Chief Investigator. Further review to be undertaken by medical experts within TMG.
- For difficult cases it may be necessary to refer to an independent neonatologist to review.

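### The protocol does not state that the bleed adjudicators or the day-28 missing-imaging reviewers are masked to arm, although the same roles advise when an infant cannot follow allocation

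*Protocol*

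**What the plan says.** **Outcome.** Protocol section 9.2.1 defines the primary outcome as "the proportion of patients who either die or develop a major or severe bleed up to and including study day 28". Death needs no grading; the bleed component does.

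**Knowledge of the arm.** Under section 5.2 the local investigator tells the consultant, the parents and the blood bank the allocation, and the allocation e-mail is filed in the infant's notes. The trial is therefore open at the site.

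**Routine grading.** Section 7.14: "The grade of bleed will be assigned centrally by means of a computer algorithm at the time of data entry".

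**Uncertain bleeds.** Section 8.2 says that "the local team may contact the joint CI or one of the neonatal medical experts", and then: "The medical experts and the joint CI will form an adjudication panel for any further clarifications if necessary (excluding the local PI". The same section sends the major bleed form to the trials unit "and without disclosing the allocation arm". I found no other statement on masking to arm.

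**No imaging within −5/+10 days of day 28.** Section 9.2.1 gives three preset rules under which no major bleed is assumed, and leaves the remainder to be settled case by case. The sequence is "Review of evidence in the first case by" the joint chief investigator, then "Further review to be undertaken by medical experts within TMG". Referral to an independent neonatologist is possible for difficult cases but not required.

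**Allocation problems.** When an infant cannot follow allocation, section 6.7 says that "the case should be discussed with the joint chief investigator or one of the medical experts".

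**The concern.** Two steps of the primary outcome rest on human judgement: uncertain bleeds, and missing-imaging cases that fall outside the preset rules. The protocol assigns both to roles that also hear about individual allocation problems, and it does not say that those people are masked or stand aside when they already know the arm. The example in section 6.7 is a clinician who thinks a higher threshold is needed, so such a conversation is likely to reveal the allocation.

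The review evidence can reveal it as well. Section 7.5 collects bleeding and transfusions on the same daily form, and the arms differ by design in when platelets are given.

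A reviewer who knows the arm can, without intending to, settle borderline calls differently in the two arms. That could move the estimated difference either way, and it would leave the primary result open to a criticism that is cheap to prevent.

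**Working it through.** **1. The steps side by side**

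| Step | Who decides | Room for judgement | Masking or exclusion stated |
|---|---|---|---|
| Death | none needed | none | not needed |
| Routine bleed grade (7.14) | central algorithm | low, given the recorded data | not needed for the algorithm |
| Major bleed form (8.2) | sent to the trials unit, then to the data monitoring committee | reporting only | arm not disclosed |
| Uncertain bleed (8.2) | joint chief investigator and medical experts | yes | local investigator excluded; masking not stated |
| Missing imaging, preset rules (9.2.1) | joint chief investigator, then medical experts | some | not stated |
| Missing imaging, all other cases (9.2.1) | the same; independent neonatologist optional | yes | not stated |

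The algorithm does not remove the judgement in the fourth row. The panel deals with how a bleed is interpreted and recorded, and that precedes the grade computed from the record. Within the preset rules, a significant deterioration is described only by examples.

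**2. The blood-product condition.** Two of the three preset rules depend on whether a deterioration led to blood products being given. A reviewer applying them must look at transfusion data, which can disclose the arm. If platelet transfusions are simply removed from the evidence, those rules may not be applicable. A remedy has to deal with both facts.

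**3. The plan's own sample size (section 9.3).** Inputs: 20% in Arm A, 12% in Arm B, two-sided 5%, 80% power. With a mean rate of 0.16:

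n = [1.960 × √(2 × 0.16 × 0.84) + 0.842 × √(0.20 × 0.80 + 0.12 × 0.88)]² / 0.08² = 328.5, so 329 per arm.

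This reproduces the stated figure. The total of 660 gives 330 per arm and 80.2% power. Nothing is wrong here.

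**4. Sensitivity to reclassified infants (illustration).** The protocol gives no rate of adjudication or missing imaging.

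- One infant reclassified in one arm: 1/330 = 0.30 points.
- Three in the same direction: 3/330 = 0.91 points, and 0.91/8 = 11% of the target difference.
- Purely as an assumed range: if 5–10% of the 660 (33–66 infants, half in each arm) were reviewed and calls were tilted by 10 percentage points in one arm, the shift would be 16.5 × 0.10/330 = 0.5 points to 33 × 0.10/330 = 1.0 point.

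The next table takes a net shift as given, at 330 per arm with the pooled two-proportion test. The type I error column assumes 20% in both arms and Arm B events lost. The power column assumes true rates of 20% and 12% and the difference shrunk.

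| Net shift (points) | Infants in one arm | Two-sided type I error | Power |
|---|---|---|---|
| 0 | 0 | 5.0% | 80.2% |
| 0.5 | 1.7 | 5.3% | 74.4% |
| 1 | 3.3 | 6.2% | 67.9% |
| 2 | 6.6 | 10.0% | 53.7% |
| 3 | 9.9 | 16.8% | 39.3% |

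The two columns show opposite directions of error. Neither predicts what will happen.

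**The case against.** The case for leaving the text alone has real weight.

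- **Most of the outcome is protected.** Death is objective. Routine grades come from an algorithm, and much of major haemorrhage grading in section 6.4 rests on measurements such as ventricular dilatation above 12 mm or echodensity above 2 cm. The panel acts only if necessary. Section 9.2.1 settles several missing-imaging cases by rule and allows independent review. This stands, and it limits the exposure to a subset of infants.
- **Masking may be set out elsewhere.** A panel procedure or the analysis plan could cover it. That is possible, but the protocol itself appoints the reviewers and states masking for the reporting form alone, so the gap is best closed there.
- **The figures are assumed.** Correct. No review rate and no tilt can be taken from the protocol. The assumed range also applies to every reviewed infant, whereas the section 6.7 route affects only infants who both prompted an allocation discussion and later needed review.

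A reader might infer three stronger things that the protocol does not support. The first is that knowledge of the arm does enter the primary outcome; the text shows only that it can. The second is that the trial has no masking of arm at all; section 8.2 withholds the arm on the major bleed form. The third is that one person both advises on and adjudicates the same infant; the overlap is of role titles, and section 6.7 names the joint chief investigator or one of several experts. Nor does anything suggest that the reviewers favour one threshold.

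**Conclusion.** The point holds in a limited form. The protocol leaves unstated whether the section 8.2 panel and the section 9.2.1 missing-imaging reviewers are masked to arm, while section 6.7 brings the same roles into allocation discussions and the evidence includes transfusions. Section 9.2.1 is the more important place, because its residual cases are openly discretionary and start with the joint chief investigator.

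The size is unknown. Each reclassified infant is worth 0.3 points, so a few calls in one direction would matter against an 8-point target. How many infants are reviewed, and whether any calls would tilt, cannot be learned from the protocol. The conclusion rests on the open design and the wording of these sections; it does not depend on the assumed rates. The change is worth making because it is cheap and removes a foreseeable criticism. The sample size is unaffected.

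**What to change.** Amend section 9.2.1 and apply the same wording to section 8.2:

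1. Reviewers work from a pack prepared by the trials unit, with the allocation, platelet counts and platelet transfusions removed. Red-cell and volume data stay, because the severe grade in section 6.4 uses them. Other laboratory results stay too, since one criterion there for a major intracranial bleed refers to laboratory derangement.
2. The trials unit applies the blood-product condition of the missing-imaging rules before review and supplies the result as yes or no, without naming the product. This keeps the rules usable. A yes/no result is not perfectly neutral between arms, but it reveals far less than the transfusion record.
3. Anyone consulted about an infant's allocation under section 6.7 does not review that infant. Another existing panel member does so, including where the joint chief investigator would have been first reviewer.
4. Each decision is recorded before any comparison by arm, and the numbers of adjudicated and assumed outcomes are reported by arm.

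The cost is a short addition to each section, a simple log of section 6.7 consultations, and a small amount of redaction by existing trials unit staff. No additional reviewer is needed, and no treatment rule changes.

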### **MAJOR BLEED FORM**

Within one working day of becoming aware of an Major Bleed, please fax a completed Major Bleed form to the  
NHSBT CTU

**[contact]**

### 8.3 Serious adverse events (SAEs)

The PI should assess all adverse events collected on the daily and weekly assessment forms for seriousness, expectedness and causality. All adverse events except major bleeds that meet the criteria for seriousness as defined below will be reported as SAEs in this trial.

A SAE is an adverse event that

- results in death
- is life-threatening\*
- requires hospitalisation or prolongation of existing hospitalisation (including readmission within 28 study days if discharged home earlier)\*\*

- results in a likelihood of persistent or significant disability or incapacity

Platelet transfusion related adverse events, as defined in 8.3.2, will also be reported as SAEs for this trial

\* The term 'life-threatening' in the definition of 'serious' refers to an event in which the patient was at risk of death at the time of the event; it does not refer to an event which hypothetically might have caused death if it were more severe.

\*\* Hospitalisation is defined as an inpatient admission, regardless of length of stay, even if the hospitalisation is a precautionary measure for continued observation. Hospitalisations for a pre-existing condition, including elective procedures that have not worsened, do not constitute an SAE.

### 8.3.1 Reporting of serious adverse events

SAE forms should be completed by the PI or other investigator (who has delegated responsibility for this task) and must be faxed to the CTU within one working day of the investigator becoming aware of the event. The CTU office will log each one and will send the SAE to the CI ([name] or delegate) according to CTU procedures. SAEs will include serious platelet transfusion related adverse events as defined in section 8.3.2.

The CI ([name] or delegate) will review all SAEs received and record his opinion, which does not overrule the opinion of the PI.

Related and unexpected SAEs must be submitted to the main REC by a CI (or by delegate) within 15 days of the CI being made aware of the SAE.

Other SAEs including related and expected events (platelet transfusion events reported to SHOT or MHRA, see below) will be submitted annually to the main REC that gave the favourable opinion for the study.

## SAE NOTIFICATION

Within one working day of becoming aware of an SAE, please  
fax a completed SAE form to the NHSBT CTU

### 8.3.2. Definitions of platelet transfusion related adverse events

Data collected on transfusion related adverse events, including platelet related transfusion related adverse events, will be based on the current definitions used by hospitals reporting to the UK national haemovigilance reporting scheme (Serious Hazards of Transfusion: SHOT and MHRA). These definitions cover the following: Incorrect Blood Component Transfused, Acute Transfusion Reactions, Transfusion-related Acute Lung Injury, and Transfusion Transmitted Infections, including bacterial transmission. The hospital site should report any platelet transfusion related adverse event to SHOT or MHRA as is normal practice.

